##### **4.9.1.1 Administration problems**

The number and proportion of patients experiencing problems with emicizumab administration at Week 1 will be provided. Details of problems will also be summarized.

##### **4.9.1.2 Exposure to Anti-coagulant factors by bleed**

The number of infusions is counted per bleed corresponding to the definition of treated bleed, i.e. all treatments that are linked to the same bleed per the 72h rule are considered to belong to the same bleed. If the same treatment/s are associated with multiple bleeds, these are counted multiple times, i.e. linked to both bleeds.

The treatments are summarized separately for bleeds which were treated with an individual coagulation factors or combinations. In addition the outputs will include a total column which includes all the data for the Prothrombin Complex Concentrate or Recombinant Factor VIIa (only and both combined). That is, the n in this analysis is the number of treated bleeds and not the number of patients. The exposure (dose/kg) by bleed is summarized by using descriptive statistics and categorically: Prothrombin Complex Concentrate (U/kg/bleed: <50, 50-100, 101-150, >150) and Recombinant Factor VIIa (ug/kg/bleed: <90, 90-180, 181-270, >270). The duration of treatment per bleed is summarized: 1, 2, 3, 4, >4. Duration of treatment per bleed is defined as time from the first to the last dose per bleed.

#### **4.9.2 Adverse Events**

Definitions of adverse events can be found in the CSP in section 5.2.

The primary objective of this study is to evaluate the overall safety and tolerability of prophylactic administration of emicizumab in patients with congenital hemophilia A who

have persistent inhibitors against FVIII at enrollment. Of primary interest in this study are the incidence and severity of all adverse events, including thromboembolic events, microangiopathic hemolytic anemia or TMA, systemic hypersensitivity, anaphylaxis, and anaphylactoid events.

Overall summaries of adverse events, serious adverse events and local injection site reactions will be presented by the number and percentage of patients having any event, having a related event, having an event leading to modification/interruption of study treatment, having an event leading to discontinuation from study, having an event leading to study treatment withdrawal, having an AESI, having a fatal AE, having grade 3 and above event. The overall number of events will also be presented.

The incidence of AEs, SAEs, AEs grade 3 and above, AEs related to study treatment, SAEs related to study treatment, AEs leading to modification/interruption of study treatment, AEs leading to discontinuation of study, AESIs, local ISRs by injection and by highest grade, fatal AEs, AEs occurring immediately after injection and AEs occurring within 24 hours after injection will be summarized. The incidence of AEs will also be summarized by highest grade.

A patient with more than one occurrence of the same adverse event in a particular System-Organ Class (SOC) or adverse event category will be counted only once in the total of those experiencing adverse events in that particular SOC or adverse event category. Any missing severity, causality, or outcome will not be imputed and classed as unknown.

Patients who died will be listed together with the cause of death.

All other information collected (e.g. action taken) will be listed as appropriate.

Only treatment emergent adverse events (starting on or after exposure to study treatment) starting on or before the end of the reporting period will be included in summaries. To define if an AE is treatment-emergent, only the date of the AE will be used (not the time). The end of the reporting period is defined as the end of the 2-year treatment period, for patients who completed the treatment, and as 24 weeks after the last dose of study treatment or 2 years after the first dose of study treatment, whichever occurs first, for patients who early discontinued from treatment. Non-treatment emergent events and AEs starting after the reporting period will be included in the patient listings and flagged but not included in the above summaries. Where an AE start date is partially or fully missing, and it is unclear as to whether the AE is treatment emergent, it will be assumed that it is.

In addition, AEs which start during follow up will be summarized in a separate single table.

Confirmed and suspected COVID-19 AEs will be listed, as well as AEs associated with COVID-19 (i.e. confirmed/suspected COVID-19 AEs and AEs with onset from -7 days to +30 days from the start of a confirmed COVID-19 AE).

Notes:

Tables presented will contain both counts of patients and events (at SOC level only). Patients who have multiple events in the same system organ class and preferred term will be counted only once in the patient counts.

AEs will be coded using MedDRA. The version of the dictionary used will be updated throughout the study.

In addition, a summary of non-serious AEs occurring in 5% or more of patients will be provided (for Disclosure purposes).

### Adverse event rate per 100 patient-years

Adverse events per patient years will be calculated for all grade AEs, SAEs, grade  $\geq 3$  AEs, TMA, thromboembolic events (TE) and TMA+TE combined. For each category of events, multiple occurrences of the same event (Preferred term) in the same patient will be counted multiple times.

The adverse event rate per 100 patient-years is computed as follows:

$$\text{AE Rate} = (\text{Number of AEs observed} / \text{Total patient-years at risk}) * 100$$

Total patient years is computed as follows:

Total patient-years at risk is the sum over patients of the time intervals (in years) between start of study therapy (study day 1) and the end of follow up or up to the cutoff whichever is earlier. This approach assumes that during an adverse event, patients remain at risk for additional events.

The 95% confidence interval for the event rate is calculated using the following method. Assume that we observe Y events over a total of T person-years at risk.

Exact confidence interval:

If  $\text{chisq}(p, df)$  is the quantile of the upper tail probability of the  $\chi^2$  distribution on df degrees of freedom, then the lower and upper bounds (LB, UB) of the exact  $(1 - \alpha/2)$  level interval are given by:

$$\text{LB} = \text{chisq}(p = \alpha/2, df = 2Y) / (2T)$$

$$\text{UB} = \text{chisq}[p = 1 - \alpha/2, df = 2(Y + 1)] / (2T)$$

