### **5.3.5.4 Persistent or Recurrent Adverse Events**

A persistent adverse event is one that extends continuously, without resolution, between patient evaluation timepoints. Such events should only be recorded once on the Adverse Event eCRF. The initial severity (intensity or grade) of the event will be recorded at the time the event is first reported. If a persistent adverse event becomes more severe, the most extreme severity should also be recorded on the Adverse Event eCRF. If the event becomes serious, it should be reported to the Sponsor immediately (i.e., no more than 24 hours after learning that the event became serious; see [Section 5.4.2](#) for reporting instructions). The Adverse Event eCRF should be updated by changing the event from "non-serious" to "serious," providing the date that the event became serious, and completing all data fields related to serious adverse events.

A recurrent adverse event is one that resolves between patient evaluation timepoints and subsequently recurs. Each recurrence of an adverse event should be recorded as a separate event on the Adverse Event eCRF.

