#### **4.6.1.1 Bleeds**

The primary analysis will be based on treated bleeds (see definition 2.2.2.2). The number of bleeds over time will be estimated using a negative binomial (NB) regression model, which accounts for different follow-up times. The time that each patient stays in the study (efficacy period) will be included as an offset in the model.

An additional model which adjusts for number of bleeds (< 9 or ≥ 9, according to eCRF) in the last 24 weeks prior to study entry will be used to support the primary analysis.

In the rare case that the negative binomial model does not converge or no bleeds were observed for a given endpoint, the primary analysis will be based on “calculated” annualized bleed rate (ABR).

The ABR is calculated using the following formula (called Calculated ABR on all outputs):

$$\frac{\text{Number of bleeds during the efficacy period}}{\text{Number of days during efficacy period}} \times 365.25$$

The efficacy analyses will include the following endpoints defined in section 2.2.2: treated bleeds, all bleeds, treated joint bleeds, treated target joint bleeds and treated spontaneous bleeds. For each endpoint, the model based ABR will be estimated along with its corresponding 95% CI. In addition, the mean, 95% CI based on Exact Poisson, median, IQR, min and max will be provided for the calculated ABR.

A corresponding listing will be provided which will include for each patient the duration of efficacy period, number of bleeds together with calculated ABR for treated bleeds, all bleeds, treated spontaneous bleeds, treated joint bleeds and treated target joint bleeds (based on data before up-titration only). A separate listing will also be provided for the up-titrated population, based on data on or after the up-titration.

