#### **4.6.5 Exploratory Efficacy Endpoints**

Analysis on 12- and 24-week interval:

Additional analysis of the calculated ABR and the number of patients with zero bleeds will be performed for 12- and 24-week intervals on treated bleeds, all bleeds, treated spontaneous bleed, treated joint bleeds and treated target joint bleeds. The 12/24-week intervals are based on the start and end of the Efficacy Period. A patient has only as many 12/24-week intervals as fully fit into this period. E.g. if the duration of Efficacy Period is 98 days (=14 weeks) he has one full 12-week interval and no full 24-week interval. A bleed is assigned to a certain 12/24-week interval based on the distance between bleed date and start of efficacy period. If a bleed is after the end of the last full interval it is not taken into account.

The calculated ABR for a 12/24-week interval will be derived using the following formula which is based on the general formula:

$$\frac{\text{Number of bleeds during the 12 or 24 – week interval}}{84 \text{ or } 168 \text{ days}} \times 365.25$$

The calculated ABRs will be summarized and a graph for the 12- and 24-week intervals for all subjects will be provided. The table will include the mean with the 95% CI based on Exact Poisson, the median with the IQR and the minimum and maximum.

The number of subjects with zero bleeds within a 12- or 24-week interval will be summarized separately and a graph for all subjects will be provided. The table will include the number and percentage of the subjects with zero bleeds and the 95% CI using the Clopper-Pearson method.

The same analysis as described above may also be performed on 36-, 48-, 60- and 72- and 98-week interval if sufficient number of patients available.

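### The 95% interval for the all-grade AE rate per 100 patient-years counts repeat events but assumes a Poisson total, so it will be too narrow; the effect is moderate for grade 3 and above and small for SAEs

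*SAP*

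**What the plan says.** SAP 4.9.2, under the heading on the adverse event rate per 100 patient-years, lists the categories: "Adverse events per patient years will be calculated for all grade AEs, SAEs, grade" 3 and above, TMA, thromboembolic events (TE), and TMA and TE combined. Within each category "multiple occurrences of the same event (Preferred term) in the same patient will be counted multiple times". The rate is total events divided by total patient-years, times 100. On the time at risk, the SAP adds: "This approach assumes that during an adverse event, patients remain at risk for additional events".

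The interval is introduced by "The 95% confidence interval for the event rate is calculated using the following method", followed by "Assume that we observe Y events over a total of T person-years at risk". Chi-square limits on 2Y and 2(Y+1) degrees of freedom, divided by 2T, then follow. Only the totals Y and T enter. The section names no dispersion parameter, robust variance or resampling.

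Protocol 5.3.5.4 feeds the count: "Each recurrence of an adverse event should be recorded as a separate event on the Adverse Event eCRF". Protocol 5.3.5.3 has severe or serious secondary events recorded in their own right, so one incident can produce several records.

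The same type of interval appears for bleeds. SAP 4.6.1.1 gives each bleed endpoint a negative binomial annualized bleed rate (ABR) with its 95% CI, and then says "In addition, the mean, 95% CI based on Exact Poisson, median, IQR, min and max will be provided for the calculated ABR". For the 12- and 24-week intervals, SAP 4.6.5 says "The table will include the mean with the 95% CI based on Exact Poisson"; no model-based interval is given there.

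**The concern.** The chi-square interval takes the variance of Y to equal its mean. That needs events to occur independently and patients to share one underlying rate. Neither is plausible for AEs: some patients report many and others none, and recurrences and linked serious events are counted one by one. The variance of Y then exceeds its mean, and limits built from Y and T alone are too close together.

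In a single-arm study with no hypothesis tests, the interval is the only statement of uncertainty attached to the rate. Rates per 100 patient-years are also easily set beside those of other studies, where limits that are too narrow can make chance differences look real.

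**Working it through.** **1. The plan's own precision figures.** SAP 2.3 and Protocol 6.1 tabulate Clopper-Pearson limits at N = 200. Beta quantiles give 0.82–5.74% for 5 patients, 2.42–9.00% for 10, 6.22–15.02% for 20 and 10.35–20.72% for 30. All four rows reproduce. They concern patients with an event. No event rate or rate interval is stated anywhere in the documents.

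**2. Inputs.** From the documents: about 200 patients and 2 years each, so T = 200 × 2 = 400 patient-years if all complete. Assumed, because the documents give neither: the mean number of events per patient m, and the spread of patient rates, taken as gamma with shape s (dispersion k = 1/s).

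**3. Formula.** The variance of a patient's count is m + k·m², so variance/mean = 1 + k·m. The true standard error of the rate is √(1 + k·m) times the Poisson value. Coverage is the probability that the SAP interval contains the true rate when Y is negative binomial. I used lower-tail chi-square quantiles, the reading under which the lower limit falls below the upper. When Y really is Poisson, that interval covers 95.1–96.1% at the rates tried, so the method itself is sound.

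**4. All-grade AEs (m = 3 to 8 over 2 years, shape 3 to 1).**

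| m | shape | variance/mean | SE ratio | coverage |
|---|---|---|---|---|
| 3 | 3 | 1 + 3/3 = 2.0 | 1.41 | 84% |
| 5 | 1.5 | 1 + 5/1.5 = 4.3 | 2.08 | 66% |
| 8 | 1 | 1 + 8/1 = 9.0 | 3.00 | 49% |

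**5. Rarer categories, over a wider dispersion range.**

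| Category, assumed rate | m | k = 0.5 | k = 1 | k = 2 | k = 4 |
|---|---|---|---|---|---|
| Grade 3 and above, 0.2 per patient-year | 0.4 | 93% | 91% | 87% | 79% |
| SAEs, 0.1 per patient-year | 0.2 | 95% | 94% | 92% | 88% |

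The step 4 shapes correspond to k between 0.33 and 1. At k = 1, grade 3 and above is still at 91% and SAEs at 94%.

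**6. What the limits would look like at k = 1.** Adjusted limits are rate × exp(±1.96·√((1 + k·m)/Y)).
- All AEs, Y = 1200, m = 6: SE = √(7/1200) = 0.076. The SAP interval is 283–317 per 100 patient-years; adjusted, 258–348 (2.6 times as wide).
- Grade 3 and above, Y = 80, m = 0.4: SE = √(1.4/80) = 0.132. SAP 15.9–24.9; adjusted 15.4–25.9 (1.16 times).
- SAEs, Y = 40, m = 0.2: SE = √(1.2/40) = 0.173. SAP 7.1–13.6; adjusted 7.1–14.0 (1.07 times).

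**7. Bleeds.** Protocol 1.2.2.3 reports, for the emicizumab arm of HAVEN 1 (N = 35), an ABR of 2.9 (1.7 to 5.0) and 62.9% of patients with no treated bleed. Assuming 24 weeks of follow-up, the mean is 2.9 × 24/52.18 = 1.33 bleeds per patient, and a common Poisson rate predicts exp(−1.33) = 26% with none. The reported interval has log-SE ln(5.0/1.7)/3.92 = 0.275; Poisson gives 1/√(35 × 1.33) = 0.146. The ratio is 1.9, so variance/mean is about 3.5; an assumed 0.65 years of follow-up gives about 5.0. A Poisson interval would therefore be too narrow for bleeds as well.

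**The case against.** The strongest reply is that little hangs on this interval. The primary endpoint is the incidence and severity of AEs. The main tables count each patient once, and the only AE interval in Protocol 6.4 is Clopper-Pearson on incidence. The rate per 100 patient-years is an addition in the SAP, and all analyses are descriptive. This stands: a reader might infer that the primary safety results are misstated, and they are not.

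Four other stronger readings also fail.
- *SAE limits are as badly wrong as all-grade limits.* The 84% to 49% range rests on 3 to 8 events per patient. At plausible SAE rates, few patients have more than one event and coverage stays close to nominal.
- *The SAP recognises overdispersion for bleeds and ignores it for AEs.* SAP 4.6.1.1 explains the negative binomial model by differing follow-up times, not by overdispersion.
- *The HAVEN 1 bleeds measure AE dispersion.* Protocol 5.2.1 excludes from AEs the non-serious bleeds consistent with pre-study disease. That calculation bears on the ABR only.
- *The ABR has no adequate interval.* In 4.6.1.1 the exact Poisson limits accompany a negative binomial CI. Only the tables in 4.6.5 rely on them alone.

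The size for AEs does depend on assumed rates and dispersion. The direction does not: any spread in patient rates, and any clustering of events, makes the interval too narrow.

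**Conclusion.** The point holds with limited reach. For all-grade AEs the 95% label will be wrong by a material amount: about 84% down to 49% coverage if patients average 3 to 8 AEs over 2 years with gamma shape 3 to 1. For grade 3 and above the effect is moderate, about 79–93% at 0.2 per patient-year, and for SAEs small, about 88–95% at 0.1, both over k = 4 down to 0.5. All of these assume 200 patients followed for the full 2 years; the rates and dispersion are assumptions. Patient-level incidence does not change, and the documents tie no decision rule to these rates. The correction is still worth making, because an interval reported as 95% should be close to that and the change is cheap.

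**What to change.** In SAP 4.9.2, name one interval for all-grade AEs, grade 3 and above, and SAEs: an intercept-only Poisson model with log patient-years as offset and robust variance clustered on patient. The point estimate stays Y/T. The squared standard error of the log rate becomes Σ(yᵢ − r·tᵢ)²/Y², where r = Y/T and yᵢ and tᵢ are each patient's events and time.

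For TMA, TE and the two combined, keep the exact Poisson interval unconditionally and print the number of patients with an event beside the number of events. The choice should not depend on whether a patient turns out to have a repeat: that would be data-driven, and a robust variance is unreliable with a handful of events. Recurrence is possible, since SAP 1.2 reports three thromboembolic events in two patients.

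For the calculated ABR, make the negative binomial CI the reported interval in 4.6.1.1. Use the robust interval in the 12- and 24-week tables of 4.6.5 where bleeds occur, and in 4.6.1.1 if bleeds occur but the model does not converge. Keep exact Poisson limits only where no bleeds are observed; there a model or bootstrap interval cannot give a usable upper limit.

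The cost is SAP wording and a standard procedure call, with no new data. The reported intervals become wider, most visibly for all-grade AEs.

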## **6.4 SAFETY ANALYSES**

The primary objective of this study is to evaluate the overall safety and tolerability of prophylactic administration of emicizumab in patients with *congenital* hemophilia A who have *persistent* inhibitors against FVIII at enrollment. Of primary interest in this study are the incidence and severity of *all* adverse events, including thromboembolic *events*, *microangiopathic hemolytic anemia* or TMA, systemic hypersensitivity, anaphylaxis, and anaphylactoid events.

All adverse events will be assessed according to the WHO toxicity grading scale. The incidence, type, and grade of adverse events will be summarized according to the primary system-organ class (SOC) and, within each SOC, by Medical Dictionary for Regulatory Activities (MedDRA) preferred term. For each adverse event, data will be provided on the timing (start and stop date, time of onset in comparison with last dose of emicizumab received, and doses of emicizumab received), severity, relationship to *emicizumab*, outcome,

and effect on therapy. The data may be presented together with two-sided 95% Clopper-Pearson CIs if appropriate.

In addition, as part of the safety evaluation, additional assessments will be summarized descriptively as follows:

- Cumulative study medication doses, dose modifications (delays and interruptions), and duration of exposure
- Compliance with respect to emicizumab intake (planned vs. received)
- Changes from baseline in physical examination findings
- Vital signs over time:
  - Vital signs will be analyzed using descriptive statistics for continuous variables and presented graphically over time with associated 95% CIs.
- Laboratory parameters (hematology and chemistry):
  - These parameters will be presented in shift tables of WHO toxicity grade at baseline versus worst grade during the treatment period. Selected laboratory parameters will be summarized in terms of mean, standard deviation, minimum, and maximum. Laboratory parameters will also be presented graphically over time, *if appropriate*.

All safety variables will be analyzed for the safety population. For each variable, the number of available observations will be reported. The safety population includes all patients who have received at least one dose of *emicizumab*.

The primary safety analysis will occur at the end of the study.

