## **4. STATISTICAL METHODS**

No formal statistical hypothesis tests will be performed and all analyses are considered descriptive.

Categorical data will be summarized using frequencies and percentages (including a category for missing, if appropriate). Continuous data will be summarized using descriptive statistics (N, mean, standard deviation, median, lower quartile, upper quartile, minimum and maximum). Other analysis methods will be specified (below) where applicable.

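### SAP 4.9.2: the exact Poisson interval for AE rates per 100 patient-years is misdefined, so as written the lower bound exceeds the upper for every count of one or more

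*SAP*

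**What the plan says.** The subsection of SAP 4.9.2 on rates per 100 patient-years covers all-grade AEs, SAEs, grade 3 and above AEs, TMA, thromboembolic events (TE), and TMA and TE combined. The rate is the number of events divided by total patient-years at risk, times 100.

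The interval is introduced with "The 95% confidence interval for the event rate is calculated using the following method" and "Assume that we observe Y events over a total of T person-years at risk". The function chisq(p, df) "is the quantile of the upper tail probability of the" chi-square distribution with df degrees of freedom, and "then the lower and upper bounds (LB, UB) of the exact" interval, labelled as level (1 - alpha/2), are:

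- LB = chisq(alpha/2, 2Y) / (2T)
- UB = chisq(1 - alpha/2, 2(Y + 1)) / (2T)

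There is no rule for Y = 0 and no factor of 100 in the bounds. Nothing elsewhere in the SAP or protocol corrects this. SAP 4.6.1.1 asks for a "95% CI based on Exact Poisson, median, IQR, min and max will be provided for the calculated ABR", and 4.6.5 also calls for exact Poisson intervals; neither gives a formula.

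**The concern.** The definition and the formulas contradict each other. An upper-tail quantile at p = alpha/2 is the 97.5th percentile, and at p = 1 - alpha/2 it is the 2.5th. The lower bound therefore takes the high percentile and the upper bound the low one.

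An inverted interval would probably be noticed in a table. Two results might not be. One is a row with zero events, where nothing looks wrong but the upper bound is far too small and overstates how firmly a risk has been excluded. The other is an inversion tidied up by sorting the two printed bounds, which gives an interval that looks plausible and is too narrow.

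Both matter most at low counts. Protocol 3.3 makes TMA and thromboembolic events a specific focus of the study. The background in protocol 1.3 reports three TMA cases, and three thromboembolic events in two patients, in the earlier Phase III trial. Zero or a handful of events is therefore a realistic table row.

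**Working it through.** **Inputs.** The definition and both formulas are from SAP 4.9.2. Alpha is taken as 0.05, because a 95% interval is promised. T is not given; I assume T = 400 patient-years (200 patients × 2 years, no dropout), the planned maximum. The SAP states no numerical interval, so there is no plan figure to reproduce.

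**Formulas compared**, each multiplied by 100 to match the rate scale:

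- As written (upper-tail): LB = 100 × [97.5th percentile, df 2Y] / (2T); UB = 100 × [2.5th percentile, df 2(Y + 1)] / (2T).
- Correct (lower-tail): LB = 100 × [2.5th percentile, df 2Y] / (2T), and 0 at Y = 0; UB = 100 × [97.5th percentile, df 2(Y + 1)] / (2T).
- Swapped: the two bounds as written, exchanged.

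**One case in full, Y = 3, T = 400.** As written, LB = 100 × 14.449/800 = 1.81 and UB = 100 × 2.180/800 = 0.27.

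**Results per 100 patient-years, T = 400:**

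| Y | Rate | As written (LB, UB) | Correct |
|---|---|---|---|
| 0 | 0 | LB undefined (df = 0), 0.0063 | 0 to 0.92 |
| 1 | 0.25 | 0.92, 0.06 | 0.006 to 1.39 |
| 3 | 0.75 | 1.81, 0.27 | 0.15 to 2.19 |
| 5 | 1.25 | 2.56, 0.55 | 0.41 to 2.92 |
| 20 | 5.0 | 7.42, 3.25 | 3.05 to 7.72 |
| 100 | 25.0 | 30.13, 20.57 | 20.34 to 30.41 |

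Reading the as-written column from right to left gives the swapped interval. At Y = 3 it is 0.27 to 1.81 against 0.15 to 2.19, too narrow on both sides. By Y = 100 the difference is small.

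**Zero events.** With 2 degrees of freedom the upper-tail quantile is -2 ln(p). As written, UB = -ln(0.975)/T = 0.0253/T; the correct value is -ln(0.025)/T = 3.689/T. The ratio is 145.7 whatever T is. At T = 300 the bounds are 0.0084 and 1.23 per 100 patient-years.

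**The inversion is general.** On the event-count scale, the printed upper bound u satisfies P(Poisson(u) ≥ Y + 1) = 0.025, and the printed lower bound l satisfies P(Poisson(l) ≥ Y) = 0.975. For Y ≥ 1, P(Poisson(u) ≥ Y) = 0.025 + P(Poisson(u) = Y) ≤ 0.025 + 0.368 = 0.393. This is below 0.975, so u < l. A numerical check for Y from 1 to 200,000 agrees.

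**Coverage**, by summing Poisson probabilities over Y:

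| Expected events | Swapped at every Y (undefined Y = 0 bound taken as 0) | Swapped for Y ≥ 1, correct row at Y = 0 | Correct |
|---|---|---|---|
| 1 | 55.2% | 92.0% | 98.1% |
| 2 | 81.2% | 94.7% | 98.3% |
| 3 | 91.7% | 96.6% | 98.8% |
| 5 | 92.8% | 92.8% | 98.0% |

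Most of the loss at 1 to 3 expected events comes from the zero-event row.

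**The level label.** Taking (1 - alpha/2) = 95% at face value means alpha = 0.10. The order is still reversed for every Y from 1 to 200,000, and the lower-tail version then covers as little as 90.1%, making it a 90% interval. The p values suit alpha = 0.05, so only the label is wrong.

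**The case against.** The printed formulas are the standard exact Poisson limits under the usual lower-tail convention, so the error lies in how the quantile is described. The names LB and UB, the word exact and the promised 95% all point to the intended reading, and a programmer using a default lower-tail function would get the right limits. If the literal version were programmed, inverted rows for common AEs would expose the fault and lead someone to the zero-event row. Nothing in the SAP says bounds will be sorted, and a plain swap at Y = 0 gives the impossible pair 0.0253 and 0 in event counts. The stakes are also limited. Protocol 6.4 bases the AE analysis on incidence, where "The data may be presented together with two-sided 95% Clopper-Pearson CIs if appropriate", and SAP 4 states that "No formal statistical hypothesis tests will be performed and all analyses are considered descriptive".

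Most of this stands, and it bounds the likely harm. The very low coverage figures should be read as the effect of the zero-event row and the swap together. What does not stand is that the matter is cosmetic: the SAP gives an explicit rule, the rule is wrong as written, and even with the zero-event row corrected the swapped interval is not the exact one. Sections 4.6.1.1 and 4.6.5 do not refer to this formula, so the error does not carry over to them automatically. It is, however, the only exact Poisson formula the SAP writes out, and the obvious one to copy.

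**Conclusion.** The concern holds. Followed literally, SAP 4.9.2 gives a lower bound above the upper bound for every Y of 1 or more. At Y = 0 it gives an upper bound about 146 times too small and no defined lower bound. Neither the inversion nor the factor of 146 depends on T; the bounds per 100 patient-years assume T = 400 and grow in proportion as T falls. The mislabelled level and the missing factor of 100 are smaller slips in the same lines.

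The rates are a descriptive supplement. Point estimates and the optional Clopper-Pearson incidence intervals are unaffected, and nothing here shows that any output is wrong. It should be fixed because the interval is the one stated for TMA and TE rates, where counts will be low and the error is hardest to see.

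**What to change.** Rewrite the interval in SAP 4.9.2 as follows:

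- Define chisq(p, df) as the lower-tail (cumulative) quantile.
- Call it a (1 - alpha) level interval with alpha = 0.05.
- LB = 100 × chisq(alpha/2, 2Y) / (2T), with LB = 0 when Y = 0.
- UB = 100 × chisq(1 - alpha/2, 2(Y + 1)) / (2T).

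Confirm that the table program uses lower-tail quantiles and the factor of 100. Useful test values at T = 400 are 0 to 0.92 for Y = 0 and 0.15 to 2.19 for Y = 3.

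The cost is a few lines of SAP text and a program check, with no change to data or design.
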